**Hypothesis 1.** Based on numerous studies, including our own pilot data, that suggest CBD may be anxiolytic and mitigate the harmful effects of THC, we hypothesize a step wise effect of strain such that the -THC/+CBD group will demonstrate the lowest anxiety, as compared to the +THC/+CBD group(s), which will have lower anxiety levels than the +THC/-CBD and non-using control groups. *In addition to strain assignment, CBD and THC blood levels will also be tested in relation to anxiety, with greater CBD levels associated with lower levels of anxiety.*

**Aim 2:** Based on the notion that CBD decreases inflammation and acute stress, the study will examine: **1) circulating inflammatory markers and 2) behavioral and biological markers of stress reactivity** in mild to moderately anxious marijuana users exposed to one of three marijuana strains: 1) +THC/-CBD, 2) +THC/+CBD, or 3) -THC/+CBD versus a matched (non-using) group.

**Hypothesis 2A.** There will be a main effect of strain such that the -THC/+CBD group will have the lowest levels of circulating peripheral inflammatory markers, as compared to the +THC/+CBD group(s), which will have lower levels than the +THC/-CBD and non-using control groups. *In addition to strain assignment, CBD and THC blood levels will also be tested in relation to inflammation, with CBD levels associated with lower levels of inflammation.*

**Hypothesis 2B.** There will be a main effect of strain such that the -THC/+CBD strain group will have the lowest levels of stress-reactivity to a laboratory stressor (measured via self-report, physiological, and inflammatory stress responses), as compared to the +THC/+CBD group(s), which will have lower levels of reactivity than the +THC/-CBD and non-using control groups. *In addition to strain assignment, CBD and THC blood levels will also be tested in relation to stress-reactivity outcomes, with CBD levels associated with less stress-reactivity.*

**Aim 3:** Based on the notion that the effects of CBD on inflammation or stress may mediate the effects of marijuana on anxiety, the study will **examine the mechanisms by which CBD influences anxiety.**

Hypothesis 3. We will estimate a mediational model that tests whether the effect of marijuana strain on anxiety is mediated by changes in circulating inflammatory markers, stress-reactivity, or both.

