**Specific Aim 2** - To assess inflammation and stress reactivity [biological and behavioral stress change scores during a stress induction (TSST)] in mild to moderately anxious marijuana users exposed to 4 weeks of use of one of three different marijuana strains compared to a group of non-using controls matched on anxiety. *Hypothesis 2A* predicts a main effect of strain such that -THC/+CBD marijuana users will have lower levels of circulating peripheral inflammatory markers compared to other marijuana groups and to non-using controls. To examine the main effects of group on these outcomes, we will estimate a random coefficient regression (RCR) models in SAS Proc Mixed wherein the summary values of the panel of inflammatory markers utilized in our preliminary study will be regressed on marijuana user group, time, and the groupXtime interaction. *Hypothesis 2A* also predicts that higher CBD levels in blood among marijuana users will be associated with lower levels of circulating peripheral inflammatory markers. The analysis for this hypothesis will again be a RCR model, but instead of group membership, the independent variables in these models will be level of CBD in blood, time, and the CBDxtime interaction. We will conduct additional models to explore whether there may also be main effects of THC in blood or a THCXCBD interaction effect on inflammatory markers. *Hypothesis 2B* predicts a main effect of strain on reduced stress reactivity. RCR models in SAS will again be utilized, wherein stress reactivity (pre-rumination induction–post rumination induction change scores of self-report, state anxiety, and inflammatory markers) will be regressed on marijuana user group. *Hypothesis 2B* also predicts that higher CBD levels in blood among marijuana users will be associated with even lower stress reactivity. As in the test of *Hypothesis 2A*, we use RCR wherein the independent variables in these models will be level of CBD in blood. As with Aim 1, we will conduct additional models to explore whether there may also be main effects of THC in blood or a THCXCBD interaction effect on stress reactivity, with appropriate Type 1 error corrections.

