**COVID-19:** Before interacting with research assistants, eligible participants will be asked additional questions related to COVID-19. These questions will be administered prior to any in-person appointment and by a research assistant over the phone (or at a distance of at least 6-feet if the participant is unable to complete the questions over the phone). These questions will be administered to protect staff and participants from the spread of COVID-19. The questions are a precaution based on current university and Centers for Disease Control and Prevention guidelines and may need to be updated as the understanding of COVID-19 evolves. These procedural questions are temporary in nature and will be lifted once university guidelines deem it unnecessary.

**Baseline Appointment (Session 1) Procedures.** Subjects who meet inclusion criteria will be scheduled for a Baseline Appointment and given instructions for the assessments, including not consuming alcohol or marijuana for 24 hours, or caffeine for 4 hours prior to coming into the lab for their sessions. After arriving at the CUChange Lab, each subject will go through the consent process and be breathalyzed to ensure a breath alcohol concentration of zero. A urine toxicology screen (and a pregnancy test for females) will also be administered to insure that subjects have not recently taken illicit drugs (and are not pregnant). Menstrual cycles and birth control use will be reported. A baseline blood draw (see details below) will be taken to quantify inflammatory biomarkers and cannabinoids. A member of our research team who has completed a certified training in phlebotomy will collect a blood sample. All blood draw procedures performed during this study will involve collecting venous blood (40 ml total/session) venipuncture of a peripheral arm vein using standard, sterile phlebotomy techniques. Subjects will then be administered the Beck Anxiety Inventory (BAI), the State Trait Anxiety Inventory (STAI), the Depression, Anxiety, and Stress Scale (DASS), and complete measures related to alcohol/drug use history, mood, stress, and quality of life and will complete cognitive testing (see Table 2 below for measures to be completed).

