After completing the final blood draw, subjects will receive training in the use of online daily assessments (see details below) and the three user groups will then be assigned a marijuana strain to use for the next four weeks instead of their typical strain. Marijuana using participants will be

randomly assigned to one of three marijuana strains (a THC-based strain akin to a typically used strain with normal levels of THC and little to no CBD, a THC and CBD strain in combination, with a 1:1 ratio between THC and CBD levels, or a CBD-enriched strain with little to no THC, and then given instructions to purchase their assigned strain (labeled either C, D, or E) at a good clinical practice local dispensary. Marijuana users will be asked to use their assigned strain (and only that strain) as they wish over the course of the next four weeks. Non-users will be asked to continue to abstain from marijuana use over the next four weeks. After completing the measures and procedures, research study staff will answer any questions subjects have on their daily messages (see details below), debrief participants, and compensate them with \$80 in cash for their time and effort during the Baseline Appointment. Lastly, each participant will be scheduled for their 2-Week (Session 2) Apppintment at the CINC for two-weeks later.

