**Blood Levels of Inflammation.** As noted in the background and in our description of our preliminary studies, we expect that CBD and THC will reduce biomarkers related to inflammation during the course of the study. Blood samples drawn at each Session will be assayed for IFNg, IL-1a, IL-1b, IL-6, IL-2, IL-4, IL-8, IL-10, IL-12, and TNF. Previous studies in animals (Mayfield et al., 2013) and humans (Bala et al., 2014), as well as our own preliminary data, suggest that cytokine activation is associated with the pathophysiology of anxiety disorders. This is the same assay used in our preliminary studies. We also expect CBD and THC to impact the responses of blood monocyte cells to a lipopolysaccharide (LPS) challenge (see details below). This may represent a more accurate test of the effects of the CBD and THC, since LPS stimulation of peripheral blood mononuclear cells (PBMCs) simulates the inflammation cascade that putatively mediates the neuroinflammatory effects of pain. To that end, 40 mL of whole blood will be drawn at each session (1-4). We will use 22 ml of blood to perform the inflammatory analysis, 10 ml of that blood for DNA extraction, and 8 ml of blood for cannabinoid analysis. There will be four blood draws total, with one during the Baseline Appointment (Session 1), one during the 2-Week Appointment (Session 2) and two during the 4-Week Appointment (Session 3 & 4 in the Mobile Van), separated by ~15 min (flower users) to one hour (edible users) for appropriate absorption. We will measure changes in cannabinoid and inflammatory levels after the long (2- and 4-week pre) and short/acute (4-week post) time course of cannabis consumption.

**DNA collection.** DNA will be extracted from 10 ml of blood (out of the total 40 ml collected) at each visit. After extraction, DNA will be quantified and stored at -80° for future analysis. DNA will be collected to look at differences in epigenetic and single nucleotide polymorphisms (SNPs) in participants with varying levels of cannabinoid content after choosing to use cannabis with high versus low THC and CBD content. The blood DNA samples collected in this study are primarily for bio-banking purposes at this time, as the analysis of these samples are expected to be performed at a future date and therefore may contribute to the current study and/or future studies.

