Daily Follow-Up Messages (Days 16-30)	Respond to brief questions (online) about cannabis use, sleep quality, and anxiety/stress management 1x/per day for 2 weeks after self-dosed cannabis use.	~2 mins/day x 15 days (~30 mins total)
4-Week Appointments (Mobile Lab)	Immediately before cannabis use (type and dose self-selected); Participant comes out to Mobile laboratory; Return completed microbiome kit, Physiological measures; Anxiety & Stress ratings; 3 rd Blood draw; Questionnaires; Cognitive & Motor Battery; Return home to self-administer edible.	60 mins
-Pre-administration Session 3		
-Post-administration Session 4	Immediately ( flower ) or 1-hour ( edible ) after self-dosing cannabis (time rage based on type of product chosen and similar drug onset time); Return to Mobile laboratory; Physiological measures; Anxiety & Stress ratings; 4 th Blood draw; Questionnaires; Cognitive & Motor Battery; Return wearable; Debriefing; Monetary Compensation; Return home.	60 mins
Monthly Follow-up Surveys (Months 2-6)	Respond to brief questions (online) about major behavioral changes (e.g., marijuana use, sleep quality, and anxiety/stress management) 1x/month for 5 months, Monetary compensation (each month).	~12 mins/month x 5 months (~60 mins total)

TOTAL TIME (6 months)	~8 hours
------------------------------	-----------------

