### **XVI. RISKS TO PARTICIPANTS**

**Risks Pertaining to the Legality of Cannabis.** The possession and use of cannabis is legal at the state level but illegal at the federal level. Any risk associated with this study is not greater than risks experienced by participants normally, since a participant in the cannabis groups must be regular cannabis users to be in the study. We will comply with all NIH guidelines, and a

Certificate of Confidentiality will be deemed applicable for our study, decreasing the risk for participants.

**Risks Associated with Venipuncture.** There is a small risk of local hematoma, infection, and syncope associated with phlebotomy. Any risk associated with undergoing four blood draws for a total of 160 ml over ~ five hours in three separate days will be minimized with certified and experienced venipuncture staff, collecting information on the subjects last meal and by offering a standard snack before the last blood draw.

**Psychological Risks and Discomforts.** While participants who use cannabis in the context of the research must already be experienced cannabis users in order to be in the study, it is still possible that some participants might experience some adverse effects from the cannabis such as changes in mood/affect, sleepiness, paranoia, and increased heart rate. There is a slight risk that using cannabis may be associated with a psychotic episode. However, participants will be monitored during the study period by the PI [name] who is a licensed clinical psychologist (Colorado license #4116) to make sure that there are no clinically significant events that occur. Increases in anxiety or discomfort will be monitored and should clinically severe or impairing anxiety be present, the participants will be removed from the study and referred to appropriate mental health treatment. This practice has been used frequently by the PI in other IRB approved studies and the risks for clinically meaningful increases in anxiety are not expected to be greater than what would be experienced in daily living. Information regarding anxiety treatment resources and appropriate referrals will be made to each participant at the end of participation, if requested.

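### Hypothesis 2B scores inflammatory change across the rumination induction, but no session with an induction has two blood draws; Session 1 reactivity also enters no described model

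*Combined protocol and SAP*

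**What the plan says.** **Outcome.** Hypothesis 2B in Section I measures reactivity through "self-report, physiological, and inflammatory stress responses". Specific Aim 2 in Section IV turns this into before-to-after induction "change scores of self-report, state anxiety, and inflammatory markers", regressed on user group. The power section plans Aim 2B with a single assessment point. Specific Aim 3 takes stress reactivity at Session 3 as a mediator, alongside Session 1-to-3 change in inflammation and, as the outcome, Session 1-to-3 change in anxiety.

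**Blood.** Section XII states: "There will be four blood draws total, with one during the Baseline Appointment (Session 1), one during the 2-Week Appointment (Session 2") and two at the 4-Week Appointment, "separated by ~15 min (flower users) to one hour (edible users) for appropriate absorption". The Baseline procedures describe "collecting venous blood (40 ml total/session"), and Section XVI counts "four blood draws for a total of 160 ml". The appointment list that closes Table 2 numbers the draws first to fourth, one per session.

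**Induction.** The Rumination Induction is run at Session 1, omitted at Session 2, and run at Sessions 3 and 4. A visual analogue scale (VAS) of anxiety and stress accompanies it. The 4-Week text places the VAS before and after the induction.

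**The concern.** A change score needs a measurement on each side of the stressor. If blood is drawn once in a session, the inflammatory response to that session's induction is not observed. One named component of Hypothesis 2B then has no data behind it, and the plan names no replacement. The practical risk is an unplanned substitute, most obviously cytokine change from Session 3 to Session 4, which would carry the acute cannabis effect.

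A second gap concerns the component that can be computed. Reactivity is measured at Session 1, before strain assignment, yet the described model has group as its only predictor. Among randomised strains this loses precision. Against the non-randomised controls, any difference in reactivity that existed before the study stays in the estimate.

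**Working it through.** **1. Reproduce the plan's blood count.** One draw × 4 sessions = 4 draws; 4 × 40 ml = 160 ml. The split in Section XII (22 ml inflammation, 10 ml DNA, 8 ml cannabinoids) sums to 40 ml. This agrees with Section XVI.

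**2. Cross draws with inductions.**

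| Session | Induction | Draws |
|---|---|---|
| 1 | yes | 1 |
| 2 | no | 1 |
| 3 (before cannabis) | yes | 1 |
| 4 (after cannabis) | yes | 1 |

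Sessions with an induction and at least two draws: 0 of 3.

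**3. Allow for unstated order.** The documents do not say whether the draw comes before or after the induction. With two orders at each of Sessions 1, 3 and 4 there are 2³ = 8 arrangements. In every one, consecutive draws that enclose an induction come from different sessions: 1 and 2 or 2 and 3 (two weeks apart), or 3 and 4. Between Sessions 3 and 4 Table 2 has participants "Return home to self-administer edible". No arrangement yields the pre-administration Session 3 score that Aim 3 uses.

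**4. Precision from the Session 1 covariate.** Analysed numbers from the power section: each strain has 75 flower + 50 edible = 125, users total 375, controls 75. Two-sided alpha .05, power .80. The noncentrality needed is 2.808.

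- Variance factor: 1/125 + 1/125 = .016, and 1/375 + 1/75 = .016, so both contrasts have the same detectable d.
- Session 3 alone: 2.808 × √.016 = .355.
- With covariate: multiply by √(1 − r²). With Session 1-to-3 change: multiply by √(2(1 − r)).

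| Assumed r | Session 3 alone | Covariate | Change |
|---|---|---|---|
| .3 | .355 | .339 | .420 |
| .5 | .355 | .308 | .355 |
| .7 | .355 | .254 | .275 |

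The documents give no Session 1–3 correlation for reactivity; their general figure between assessments is .50.

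**5. Prior difference against controls (375 v 75).** Assume a stable difference δ (in SD) at both sessions and no true effect. Session 3 alone has noncentrality δ/√.016. The covariate model leaves δ(1 − r), with noncentrality δ(1 − r)/√(.016(1 − r²)). At δ = .30 and r = .5 these are 2.37 and 1.37. Rejection rates at nominal 5%:

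| δ (assumed) | Session 3 alone | Covariate, r = .5 |
|---|---|---|
| 0.05 | about 7% | about 6% |
| 0.10 | about 12% | about 7% |
| 0.20 | about 35% | about 15% |
| 0.30 | about 66% | about 28% |

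Under the same assumption, Session 1-to-3 change removes δ and rejects at about 5%.

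**The case against.** **The draws may enclose an induction.** A reader might infer that no induction has blood on both sides of it in any sense. The documents do not support that: depending on order, the Session 3 and 4 draws can enclose an induction, and controls take no cannabis in between. What stands is narrower. No two draws fall within one session, and the Session 3–4 pair differs between users and controls by the acute cannabis exposure itself.

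**There may be more than one baseline draw.** Section XII says "After completing the final blood draw, subjects will receive training in the use of online daily assessments", which could imply several. The explicit counts outweigh it, and a second baseline draw would still leave no pair at Session 3. The wording should nonetheless be reconciled.

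**One time point is a stated choice.** The power section does plan Aim 2B with one assessment point, so the single outcome session is deliberate. It does not prevent a baseline covariate, and the plan gives no reason to leave out a measure it already collects.

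**The controls are matched.** They are matched on anxiety (GAD-7 of at least 5), and Table 2 allows baseline differences in BDI-II and BAI to be covaried if necessary. This makes a large prior difference less likely, but neither provision covers reactivity. The equivalence tests on pretest measures check balance and adjust nothing.

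**Change scores are not clearly better.** This stands. They are less precise than the existing plan at r = .3, no better at r = .5, and remove a prior difference only if it is stable. The covariate model leaves part of a stable difference. Statisticians can reasonably differ on which should lead.

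**Conclusion.** The inflammatory component of Hypothesis 2B cannot be computed as written: 0 of 3 induction sessions has a within-session blood pair. This rests on the documents' own counts and needs no assumption. It would be wrong to infer that Hypothesis 2B as a whole is untestable. The VAS supplies the self-report component, and Aims 1 and 2A are unaffected. State anxiety is unresolved, because Specific Aim 2 does not say whether it means this VAS or the STAI. Table 2 lists the STAI under baseline only, while Table 1 and the Section XII text say baseline measures are repeated.

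The unused Session 1 reactivity is a smaller point. Among randomised strains it costs precision only: detectable d of .355 against .339 to .254 over assumed r of .3 to .7. Against controls, the bias depends on a prior difference that the documents do not give. A reader might seize on the 66% false-positive rate, but that is the top of an assumed range that begins at about 7%, so it is not an estimate for this trial. Figures 3a and 3b are not visible, so the statement about Aim 3 rests on its text.

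**What to change.** 1. Remove inflammatory change from the stress-reactivity definition in Hypothesis 2B (Section I) and Specific Aim 2. Keep circulating markers in Aim 2A. State that Session 3-to-4 cytokine change will not be used as stress reactivity.
2. Define reactivity as the before-to-after Rumination Induction VAS change at Session 3, on one stated scale. The 4-Week text gives 1–100 and Table 2 gives 0–10.
3. Replace TSST in Specific Aim 2 with the Rumination Induction. Reconcile the reference to a final baseline draw with the four-draw count. State whether state anxiety is the VAS or the STAI, and when the latter is given.
4. Add Session 1 reactivity as a covariate in the Aim 2B model.
5. For contrasts with controls (Aim 2B, Models 3a and 3b), use the covariate model and report Session 1-to-3 change in reactivity as a sensitivity analysis. Acknowledge that matching was on GAD-7 and not on reactivity.

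The cost is wording and model specification, with no new draw, visit or participant. The inflammatory part of Hypothesis 2B is given up. Keeping it would need at least one extra draw: five draws for Session 3 alone, or 200 ml at 40 ml each. The Spring 2023 update describes contacting people who have already completed the study, so any definition changed after data collection should be recorded as such.

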**Specific Aim 3** - To test indirect effects of marijuana use on anxiety (BAI) via inflammatory markers and stress reactivity in anxious marijuana users exposed to 4 weeks of use of one of three different marijuana strains compared to a group of non-using controls matched on anxiety. Hypothesis 3 will test mediational models that ask whether the effect of marijuana use and strain on anxiety is mediated by changes in inflammation, stress reactivity, or both. To this end, we will estimate the mediational models in Figures 3a and 3b via structural equation modeling. To test the overall effect of use of marijuana versus non use, we will estimate model 3a wherein the sole exogenous variable is marijuana users (coded as 1) versus non-users (coded as 0). The mediators will be change in inflammation from Session 1 to Session 3 and stress reactivity at Session 3. The outcome variable is change in anxiety from Session 1 to Session 3. This model will be estimated and both the fit of the model and the significance of the path coefficients will be examined. Importantly, we will compare the path coefficients from user status to inflammation versus stress reactivity to determine whether use is associated with changes in inflammation, stress reactivity, or both. Assuming that the paths from inflammation and stress reactivity to anxiety are significant, we can test whether there are indirect effects of user status on anxiety that are mediated by inflammation, stress reactivity, or both. A test for completeness of mediation is employed through a 1 degree of freedom  $\chi^2$  test where a path directly from user status to anxiety is added to the model. A nonsignificant direct path and a nonsignificant change in  $\chi^2$  suggest that user group effects on the anxiety were mediated through the theoretical mediational constructs. A secondary test of mediation will utilize bootstrap methods to test the significance of, and confidence limits around, the mediated effect. Similar mediational analyses have been widely used by Co-I [name]. The model depicted in Figure 3b will test the more focused hypothesis that the ratio of cannabinoids is critical for the biological and behavioral changes that drive anxiety. The analysis will follow identical procedures to those described to test Model 3a. Finally, it is also possible to use continuous values of THC and CBD in blood as the exogenous predictors in the model.

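### Aim 3 reads a nonsignificant direct path as suggesting mediation without first requiring a user-to-mediator path or an indirect effect to be shown

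*Combined protocol and SAP*

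**What the plan says.** All of this is in section IV, Statistical Analysis Plan, Specific Aim 3. Model 3a has user status (1 or 0) as its only exogenous variable and change in anxiety from Session 1 to Session 3 as its outcome. On the mediators it says: "The mediators will be change in inflammation from Session 1 to Session 3 and stress reactivity at Session 3". The steps then run in this order:

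1. The model is estimated and "both the fit of the model and the significance of the path coefficients will be examined".
2. The user-to-mediator paths are compared "to determine whether use is associated with changes in inflammation, stress reactivity, or both".
3. "Assuming that the paths from inflammation and stress reactivity to anxiety are significant, we can test whether there are indirect effects" of user status, through either mediator or both. No method is named here.
4. "A test for completeness of mediation is employed through a 1 degree of freedom" chi-square, after a direct path is added. A nonsignificant direct path and a nonsignificant chi-square change are said to "suggest that user group effects on the anxiety were mediated through the theoretical mediational constructs".
5. "A secondary test of mediation will utilize bootstrap methods", giving significance and confidence limits for the mediated effect.

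For Model 3b, which carries the cannabinoid-ratio hypothesis: "The analysis will follow identical procedures to those described to test Model 3a".

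**The concern.** An indirect effect is the product of two paths: user status to mediator (a) and mediator to anxiety (b). The direct path is a different parameter. Finding it nonsignificant leaves the product undetermined: a could be zero and the result would look the same. The nonsignificant coefficient and the nonsignificant 1-df chi-square test the same restriction on the same data, so they are not two pieces of evidence.

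Step 4 is nevertheless the only place where the Aim 3 text says which result supports mediation. The one written condition before it is that the b paths are significant. Neither a significant a path nor a significant indirect effect is required, although steps 1 to 3 and 5 would supply both.

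Aim 3 is meant to show how CBD influences anxiety. Applied as written, the sentence could attach a mechanism to a result in which cannabis use did not change the mediators.

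**Working it through.** **The plan's own figure.** The Power Analysis paragraph requires 450 participants for the mediation models: 4 × 75 + 3 × 50 = 450, that is 375 users and 75 controls. Its Monte Carlo result cannot be rerun, because Table 3 and Figure 3b are not in the available text. For a single standardised path of .20, Fisher's z gives power Φ(atanh(.20) × √447 − 1.96) = Φ(4.29 − 1.96) = .99 at N = 450; .80 is reached at N = 194. This is consistent with the stated .80 or better.

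**Assumptions.** The documents estimate none of the following: two independent mediators; equal standardised b paths; real mediation means a = .20 for both mediators (the plan gives .20 for the Model 3b contrasts to stress reactivity; I borrow it for Model 3a). The SD of user status is √(375/450 × 75/450) = .373, so a standardised direct effect of .05 is .05/.373 = 0.13 SD and .10 is 0.27 SD.

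**Rule as written.** Both b paths significant at .05, direct path |t| < 1.96, and likelihood-ratio chi-square < 3.841; 6,000 simulated trials per cell. Share of trials in which it is met:

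| b | Direct effect | a = 0 (no mediation) | a = .20 (real mediation) |
|---|---|---|---|
| .3 | 0 | 95.5% | 94.9% |
| .3 | .05 | 77.9% | 78.0% |
| .3 | .10 | 35.4% | 35.9% |
| .2 | 0 | 93.9% | 93.0% |
| .2 | .05 | 78.5% | 79.6% |
| .2 | .10 | 38.9% | 41.4% |
| .1 | 0 | 30.0% | 29.1% |
| .1 | .05 | 26.2% | 35.1% |

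Hand check of the second row at a = 0: residual variance 1 − 2 × .3² − .05² = .8175; SE = √(.8175/450) = .0426; .05/.0426 = 1.17; Φ(1.96 − 1.17) − Φ(−1.96 − 1.17) ≈ .78. With the mediators correlated .3 (b = .3, no direct effect) the rates are 94.2% v 95.6%.

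**Where the rule does protect.** At b = 0 it is met in 0.3% of trials or fewer. It also rejects large unmediated effects. The total effect under mediation is 2 × .20 × b, which is .12 at b = .3 and .08 at b = .2. If the same total is entirely direct, the rule is met in 19% and 56%, against 95% and 93% under mediation. With the plan's paths of .40 and .20 the totals are .18 and .12, and the unmediated rates are 0.8% and 23%.

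**Adding the missing condition.** Require also at least one significant a path. With a = 0 and no direct effect, the expected rate is about (1 − .95²) × .95 = .093; simulation gives 8.5–9.7%. Under real mediation the rule is still met in 95% (b = .3) and 93% (b = .2).

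**Testing the indirect effect itself.** With a 97.5% interval per mediator the chance of any false claim is about 1 − .975² = .049. The percentile bootstrap (2,000 resamples) gives 5–6% false claims and 99.9–100% detection at b = .2–.3, and 68% at b = .1. Requiring a and b of the same mediator both to be significant at .025 gives 4.6–5.2%, 99.8–100% and 67%.

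**Completeness.** For 375 v 75, SE = √(1/75 + 1/375) = .126 SD. Power for a direct effect of 0.2, 0.3 and 0.4 SD is Φ(d/.126 − 1.96) = .35, .66 and .89. A direct effect of 0.2 SD would therefore be missed in about 65% of trials, so nonsignificance is weak evidence even of complete mediation.

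**The case against.** The strongest defence is to read the steps in order. Path significance is examined, the user-to-mediator paths are compared, indirect effects can be tested, and only then comes a step named for completeness, whose job is to separate full from partial mediation. The wording is cautious, and a bootstrap with confidence limits is planned. Once a significant user-to-mediator path counts, the contrast is about 9% v 93–95%, which is serviceable. The cells near 95% with no mediation contain no effect on anxiety at all, and Aim 1 tests group effects on anxiety separately. If the sentence presupposes a significant total effect, the no-mediation rates fall to 1–4%, although real full mediation is then recognised in only 70% (b = .3) or 37% (b = .2).

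Much of this stands as an account of how a careful analyst would proceed. It does not remove the defect, because none of these conditions is written and the mediation reading is attached to step 4 alone.

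Three stronger readings are tempting, and the documents do not support them:

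- A reader might infer that the plan cannot tell which mediator carried an effect. Only the completeness step gives one verdict for both; steps 2 and 3 address inflammation and stress reactivity separately.
- A reader might infer that the indirect effect goes untested. The plan says it can be tested and names the bootstrap; the issue is its rank and that no conclusion depends on it.
- A reader might infer that N = 450 is too small for the mediated effect, because the power statement concerns the smallest path. Under the assumptions above, detection is 99.9–100% at b = .2–.3.

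**Conclusion.** The concern holds as a missing condition in an inference rule. For b of .2 to .3, the written condition plus the completeness result is met about equally often with and without a group effect on the mediators: 93–95% with no direct effect and about 78–80% at a standardised direct effect of .05. This should not be read as a 95% false-claim rate for the whole Aim 3 analysis. It describes only the condition and result that the plan ties to the mediation sentence, and the other planned steps would catch most such cases if they were made binding.

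The figures rest on assumed effects, two equal and independent mediators (little changed at a correlation of .3), and Model 3a. Model 3b inherits the rule, but its figure is not shown, so the rule was not simulated with its contrasts. The change should be made: the inference is unsound as worded, and the plan already contains the remedy.

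**What to change.** In Specific Aim 3:

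- Delete the inference from a nonsignificant direct path and chi-square change to mediation.
- Make the indirect effect through each mediator the Aim 3 test in Models 3a and 3b. Use the bootstrap interval already planned, with multiplicity control over the two mediators (for example 97.5% each). Claim mediation through a mediator only when its interval excludes zero. A joint test of both paths of that mediator at .025 would serve equally well.
- Report the direct effect with its confidence interval as a description, and do not claim complete mediation from nonsignificance.

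The cost is SAP wording; no new data or methods are needed. The complete-mediation claim is given up. If the mediator-to-anxiety paths are weak (b = .1), at least one mediator is detected in only about 67–68% of trials.
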